6.4. MULTIPLE COMPARISONS AND MULTIPLICITY

No formal statistical comparisons will be performed in this study.

Sponsor: Aimmune Therapeutics, Inc.

Protocol: ARC0004

Version: Version 1.0, 10Jul2019

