It has been previously observed that AR101 was well tolerated and appeared to reproducibly induce desensitization to peanut when used daily. The goal of ARC004 is to examine whether intermittent dosing of AR101 during extended maintenance can preserve the desensitization gained by daily dosing; and if so, how much daily treatment is advisable before the interval can be adjusted. In the short term, the data gained from this study should provide very practical guidance to assist physicians in determining how to manage short-term dosing interruptions. Longer term, the results will have key implications for designing maintenance therapy regimens in future AR101 development protocols.

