Upon entry into the EM phase of the study, Group 2 subjects will be consecutively enrolled into 1 of several cohorts that will conditionally explore an alternate dosing interval regimen over 28-week study periods, as follows:

1. EM Cohort 1: The first 120 Group 2 subjects to enter ARC004 will comprise Cohort 1, and will continue 300 mg of AR101 QD for 28 weeks before undergoing an Exit DBPCFC (total 28 weeks).
2. EM Cohort 2: The next 50 Group 2 subjects (subjects 121-170) enrolling in ARC004 will comprise Cohort 2 and will take 300 mg of AR101 QOD for 4 weeks and then BIW (eg, Monday/Thursday) for 24 weeks (total of 28 weeks) as tolerated, before undergoing an Exit DBPCFC.
3. EM Cohort 3: All remaining subjects recruited into ARC004 (subjects 171 to the end) will comprise Cohort 3. This cohort will be randomized 1:1:1 to 1 of 3 initial strategies:
 - a. 300 mg QD for 56 weeks followed by an Exit DBPCFC (Cohort 3A) (total 56 weeks)
 - b. 300 mg QD for 28 weeks, then 300 mg QOD for 4 weeks, then BIW for 24 weeks, as tolerated, followed by an Exit DBPCFC (Cohort 3B) (total 56 weeks)
 - c. 300 mg QD for 28 weeks, then 300 mg QOD for 4 weeks, then BIW for 24 weeks, then 300 mg QW for 28 weeks, as tolerated, followed by an Exit DBPCFC (Cohort 3C) (total 84 weeks)

In ARC004, Exit DBPCFCs will test to a maximum of 4043 mg cumulative peanut protein to determine the continued efficacy of each alternate dosing schedule. Following the end-of-study visit, each subject's participation in ARC004 ends. The end of the study is defined as the date of the last visit of the last subject.

End of Participation in ARC004 and Entry into ARC008: After the end of participation in ARC004, subjects may enroll in the long-term, open-label extension study ARC008 to continue treatment with AR101 at their current dosing regimen (QD, BIW, QW, or QOW) or switch to AR101 daily dosing, until AR101 becomes commercially available or ARC008 is terminated, as follows:

- Subjects on any dosing regimen able to tolerate at least the 600 mg single dose of peanut protein (≥ 1043 mg cumulative) at their ARC004 Exit DBPCFC will continue their current dosing regimen in Treatment Pathway 1 of ARC008 when that study is available. If ARC008 is not available at the study site, these subjects may continue their current dosing regimen and have visits in ARC004 until they can enroll in ARC008.

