9 STATISTICAL CONSIDERATIONS

This protocol outlines the major statistical considerations for the ARC004 study. Full details on the statistical methodology to be used in the analysis and data handling for this trial will be described in the statistical analysis plan (SAP) to be developed prior to database lock and statistical analysis.

Data will be summarized using descriptive statistics within treatment group and cohort. No specific hypothesis testing or comparisons between the treatment groups is planned for this study. Details of within group and within cohort comparisons relative to baseline values and exploratory comparisons between cohorts will be described in the SAP.

Descriptive statistics will be presented in the following manner:

- Continuous data (ie, age, body weight, and height) will be summarized descriptively by mean, standard deviation, median, and range.
- Categorical data (ie, sex and race) will be presented as enumerations and percentages.

Data will be summarized by treatment group, cohort, and treatment phase (as defined in [Section 3.1](#)).

Data will be summarized in tables for each treatment group, treatment groups combined, and treatment phase (as defined in [Section 3.1](#)).

Data from ARC003 will be combined with ARC004 and will be used to define baseline, as appropriate. Additional details about combining data and handling varying exposure times will be described in the SAP. Data will be listed for each subject.

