Group 2 (former AR101): Subjects who complete the AR101 arm of ARC003 and tolerate a challenge dose of ≥ 443 mg cumulative of peanut protein at the ARC003 Exit DBPCFC are eligible to enroll in ARC004. Group 2 subjects will have undergone the Initial Dose Escalation, Up-dosing, and Maintenance Periods in ARC003 and will therefore enter the ARC004 EM period directly.

Upon entry into the EM phase of the study, Group 2 subjects will be consecutively enrolled into 1 of several cohorts that will conditionally explore an alternate dosing interval regimen over 28-week study periods, illustrated in [Figure 1](#) and as follows:

EM Cohort 1: The first 120 Group 2 subjects to enter ARC004 will comprise Cohort 1, and will continue 300 mg of AR101 QD for 28 weeks before undergoing an Exit DBPCFC (total 28 weeks).

EM Cohort 2: The next 50 Group 2 subjects enrolling in ARC004 will comprise Cohort 2 and will take 300 mg of AR101 QOD for 4 weeks and then BIW (eg, Monday/Thursday) for 24 weeks (total of 28 weeks) as tolerated, before undergoing an Exit DBPCFC.

EM Cohort 3: All remaining subjects recruited into ARC004 will comprise Cohort 3. This cohort will be randomized 1:1:1 to 1 of 3 initial strategies:

- a. 300 mg QD for 56 weeks followed by an Exit DBPCFC (Cohort 3A) (total 56 weeks)
- b. 300 mg QD for 28 weeks, then 300 mg QOD for 4 weeks, then BIW for 24 weeks, as tolerated, followed by an Exit DBPCFC (Cohort 3B) (total 56 weeks)
- c. 300 mg QD for 28 weeks, then 300 mg QOD for 4 weeks, then BIW for 24 weeks, then 300 mg QW for 28 weeks, as tolerated, followed by an Exit DBPCFC (Cohort 3C) (total 84 weeks)

[figure not shown]
In ARC004, Exit DBPCFCs will test to a maximum of 4043 mg cumulative peanut protein to determine the continued efficacy of each alternate dosing schedule. Following the end-of-study visit, each subject's participation in ARC004 ends. The end of the study is defined as the date of the last visit of the last subject.

As per the study design, if subjects were on any other regimen other than QD and were tolerating it well during ARC003, those subjects were allowed to continue on their regimen in ARC004. As per the safety monitoring committee suggestion, all subjects in group 2

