11. CHANGE FROM ANALYSIS PLANNED IN PROTOCOL

The analysis methods and summaries detailed in the SAP include, but are not limited to, all analyses included in the Statistical Considerations section of the protocol, with the following exceptions:

- Baseline for DBPCFC is defined as the Exit food challenge from ARC003 for both Group 1 and Group 2 subjects.
- For secondary endpoints relating to post-maintenance DBPCFC, only Group 1 post-maintenance DBPCFC results will be summarized. Group 2 Exit ARC003 food challenge data will not be summarized in ARC004 as post-maintenance.
- Post-maintenance DBPCFC as referenced in the protocol will be referred to as maintenance DBPCFC in this document and all corresponding outputs.

Any deviations from the plans detailed in this SAP will be described and justified in the final clinical study report. A separate document to this SAP will provide a table of contents and mockups for the expected layout and titles of the TLFs. Any changes to format, layout, titles, numbering, or any other minor deviation will not necessitate a revision to the SAP nor will it be considered a deviation from planned analyses. Only true differences in the analysis methods or data handling will necessitate such documentation.

Sponsor: Aimmune Therapeutics, Inc.

Protocol: ARC0004

Version: Version 1.0, 10Jul2019

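### The SAP specifies none of the exploratory between-cohort comparisons the protocol promised, so the randomised daily versus twice-weekly contrast (3A vs 3B) has no prespecified estimate or interval

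*SAP*

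**What the plan says.** - **The commitment.** Protocol Section 9 says that "exploratory comparisons between cohorts will be described in the SAP"; the synopsis (Statistical Considerations) makes the same commitment. Section 9 also rules out hypothesis testing and comparisons between the treatment groups.
- **The design.** On Cohort 3, SAP Section 2.3 states: "This cohort will be randomized 1:1:1 to 1 of 3 initial strategies". Protocol Section 6.1 assigns this randomisation to the interactive response system. Under Protocol Section 3, 3A takes the daily dose for 56 weeks. 3B takes it daily for 28 weeks, every other day for 4 and twice weekly (BIW) for 24, also 56 weeks. Both finish with an Exit DBPCFC. Cohorts 1 and 2 were not randomised: "Group 2 subjects will be consecutively enrolled into 1 of several cohorts".
- **The planned analysis.** SAP Section 6.4: "No formal statistical comparisons will be performed in this study". Section 6.2 excludes modelling. Section 9.1.1 gives response rates with Clopper-Pearson 95% intervals within each group or cohort, and Section 9.1 restricts DBPCFC summaries to completers aged 4 to 17. No difference or ratio between cohorts is specified anywhere.
- **The declared changes.** SAP Section 11 says that the SAP includes "all analyses included in the Statistical Considerations section of the protocol, with the following exceptions". The exceptions concern only the DBPCFC baseline and the definition and naming of the post-maintenance challenge.

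**The concern.** Protocol Section 1.3 gives the aim as "to examine whether intermittent dosing of AR101 during extended maintenance can preserve the desensitization gained by daily dosing". One natural reading of that question is comparative, and randomising Cohort 3 gives the design a way to answer it over equal treatment time. As the SAP stands, nobody has fixed in advance which cohorts are contrasted, in which subjects, or how a missing exit challenge is handled. Any difference reported later would have to be labelled post hoc under SAP Section 6.1.

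The planned rates cannot stand in for the contrast. Under Protocol Sections 3.1.5 and 6.3.7, subjects who do not tolerate nondaily dosing, and those who switch to daily dosing after missing a nondaily dose for more than 3 days, omit the exit challenge. The SAP's Completer population (Section 4.2) requires, for Group 2, an evaluable exit challenge. Failures of the nondaily regimen therefore leave the denominator in 3B with no counterpart in 3A. Yet Protocol Section 3.1.5 says that subjects meeting the nondaily failure criteria count as treatment failures in each cohort's analysis. SAP Section 7.4.2 does class anyone who cannot be called a responder as a non-responder, but a table limited to completers never applies that rule to these subjects.

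**Working it through.** 1. **The plan's own figure.** The only design calculation for ARC004 is an 80% chance of seeing at least one AE with about 400 subjects and a rate of 4 per 1,000 (Protocol 9.4). 1 − (1 − 0.004)^400 = 0.799, so it reproduces. It does not bear on the cohort contrast; the protocol gives no efficacy power.

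2. **Arm size.** Protocol 7.8.3 plans 175 subjects in Cohort 3: 175/3 ≈ 58 per arm. As a lower case, Protocol 9.4 assumes 400 subjects in ARC004. If the 3:1 ratio carries over, 300 are active rollovers, and (300 − 120 − 50)/3 ≈ 43 per arm.

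3. **Response rates.** Protocol 1.2.2 reports that 100%, 90% and 60% of ARC002 subjects tolerated 443, 1043 and 2043 mg cumulative on daily dosing. These correspond to the 300, 600 and 1000 mg responder definitions in SAP 7.4.1. ARC002 gives no rate for 2000 mg. The 80% row below is an assumption.

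4. **Precision of 3A minus 3B.** Half-width = 1.96 × √(2p(1 − p)/n), with equal true rates:

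| p | n = 58 | n = 43 |
|---|---|---|
| 0.90 | 1.96 × √(0.18/58) = 10.9 points | 12.7 points |
| 0.80 | 1.96 × √(0.32/58) = 14.6 points | 1.96 × √(0.32/43) = 16.9 points |
| 0.60 | 1.96 × √(0.48/58) = 17.8 points | 1.96 × √(0.48/43) = 20.7 points |

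At 100% response this formula returns zero, which is one reason to prefer Newcombe. With 58/58 in both arms the Wilson lower limit is 58/(58 + 3.84) = 0.938, so the Newcombe interval is about ±6.2 points.

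5. **What the arms could detect.** With a two-sided 5% test of two proportions (pooled variance under the null), 58 per arm has 80% power for a drop of 20.7 points from 90%, or 25.7 points from 60%.

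6. **Why completer rates mislead.** The counts here are assumed. Of 58 per arm, 3 in 3A and 10 in 3B have no exit challenge, and about 90% of those challenged respond.
   - Completers: 50/55 − 43/48 = 90.9% − 89.6% = 1.3 points.
   - All randomised, no challenge counted as non-response: 50/58 − 43/58 = 86.2% − 74.1% = 12.1 points. Wilson limits are 0.751 to 0.928 and 0.616 to 0.837. Newcombe lower limit: 0.121 − √[(0.862 − 0.751)² + (0.837 − 0.741)²] = −0.026. Upper limit: 0.121 + √[(0.928 − 0.862)² + (0.741 − 0.616)²] = 0.262. The interval is −2.6 to 26.2 points.
   - With 6 or 15 unchallenged in 3B instead of 10, the all-randomised difference is 5.2 or 19.0 points; the completer difference stays below 1 point.

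7. **Adding 3C.** 3A against 3B plus 3C (58 vs 117) gives half-widths of 9.4 points at 90% and 15.4 at 60%.

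**The case against.** Several parts of the case on the other side stand.

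- A reader might infer that SAP 6.4 contradicts the protocol. It does not: Protocol Section 9 itself excludes hypothesis testing and comparisons between treatment groups. Those groups are, however, the former-placebo and former-AR101 arms, and Section 9 treats exploratory cohort comparisons separately. An interval without a test respects both statements. The defect is the undeclared omission.
- A reader might infer that the daily versus BIW difference will never be known. The rates for 3A and 3B will appear side by side, and SAP 6.1 allows documented post-hoc analyses. What is missing is a prespecified estimate and interval in a suitable set.
- A reader might call 3A vs 3B the only unbiased contrast. 3C is randomised too. SAP 2.3 reports that 3C subjects on BIW were to stay on it, SAP 6.1 that no weekly dosing began, and SAP 7.7 already pools 3B with 3C for events. Nor is an open-label comparison under regimen-specific rules free of bias. Protocol 7.8.2 discontinues nondaily subjects after one related severe AE or two related moderate ones, among other triggers, while Protocol 6.5.7 refers daily subjects to the Up-dosing dose-adjustment procedures. Counting no challenge as non-response is also wider than Protocol 7.8.3, which counts early discontinuations due to AEs.
- A reader might infer that the study's goal depends on this one difference. Protocol 1.3 also asks how much daily treatment should precede a longer interval, which 3A vs 3B does not address. SAP 9.1 looks at change from each subject's own ARC003 exit challenge.
- The nondaily data are described as exploratory, and the primary endpoint is safety. That argues against a test, not against an interval.

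**Conclusion.** The point holds as a gap between protocol and SAP. A promised class of analysis is absent, Section 11 does not say so, and the randomised 56-week contrast is left without a prespecified estimate. It is worth correcting, but it does not touch the primary endpoint and does not make the planned tables wrong for describing completers.

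At the planned size the interval would be about ±11 points at 90% response and ±18 at 60%, so only large differences would be resolved. This rests on 58 randomised per arm and on ARC002 rates applying to both arms. The analysed number may be smaller, since the DBPCFC summaries are limited to ages 4 to 17. The example in step 6 shows that completer rates can hide a difference; it does not predict that they will. The documents do not support saying that this contrast is the only unbiased one or that the study's question is otherwise unanswered.

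**What to change.** Add to SAP 9.1.1 a table of the 3A minus 3B difference in 300, 600, 1000 and 2000 mg response at the Exit DBPCFC, with 95% Newcombe intervals, labelled exploratory and with no test:

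- **Main set:** all randomised and treated Cohort 3A and 3B subjects, with no exit challenge counted as non-response.
- **Sensitivity analysis:** completers.
- **Age:** state whether adults are included or the set is limited to 4 to 17 years.
- **Interpretation:** note that the non-response rule partly reflects the stricter discontinuation rules for nondaily dosing. The main analysis therefore estimates success of the regimen strategy, and not desensitisation alone.
- **Optional support:** 3A vs 3B plus 3C, with the timing of the 3C exit challenge stated, since the SAP does not give it after 3C was held on BIW.

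In Section 11, declare any between-cohort comparison still not planned, with the reason. If the sponsor prefers no comparison at all, declaring and justifying that there would remove the inconsistency, but would leave the contrast unestimated. The cost is one table; it needs no new data and spends no alpha.

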6.5. SIGNIFICANCE LEVEL

Unless stated otherwise, all CIs will be calculated at the 95% level and provided for descriptive purposes only rather than formal statistical inference.

7. DATA HANDLING METHODS

7.1. VISIT WINDOWS

All information will be listed, summarized, and analyzed according to the nominal visit time point, study period, or dose. No visit windowing will be performed.

7.2. DATA PRESENTATION

Individual subject data listings will be provided to support summary tables and serve as a data source. Unless otherwise noted, all data collected during the study for all enrolled subjects will be included in data listings.

Unscheduled visits will be listed but not included in by-visit summaries. Results from unscheduled visits may be used as baseline values and for other derivations not tied to visit names (for example, unscheduled visits are included in the determination of worst post-baseline values for laboratory results).

7.3. MAXIMUM TOLERATED DOSE AT DBPCFC

The maximum tolerated dose (MTD) for a DBPCFC is defined as the maximum single dose of peanut protein resulting in no more than mild symptoms and determined to have been tolerated (i.e., the subject did not experience any dose-limiting symptoms). Any symptom requiring treatment is inherently dose-limiting; thus, a dose during a DBPCFC cannot be considered “tolerated” if treatment was deemed necessary by the investigator. The MTD at the ARC003 Exit DBPCFC will be used as the baseline amount of peanut protein tolerated. If a subject is administered non-standard doses at a DBPCFC, the MTD will be considered as the highest standard dose (whether administered or not) that is less than the highest tolerated non-standard dose.

When describing the MTD at the Exit DBPCFC, in terms of the cumulative amount of peanut protein, the 1 mg dose will not be included. Thus, subjects who tolerate all dose levels from 3 mg to 300 mg or 1 mg to 300 mg have a cumulative MTD of 443 mg.

Sponsor: Aimmune Therapeutics, Inc.

Protocol: ARC0004

Version: Version 1.0, 10Jul2019

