3.1.4 Maintenance

Subjects entering the Maintenance Period will continue AR101 300 mg once daily, undergoing directly observed dosing at 12 and 24 weeks. Down-dosing may be necessary during the Maintenance Period due to safety or tolerability reasons, but such subjects will remain in the Maintenance Period even if they are temporarily taking a dose of less than 300 mg. The duration of the Maintenance Period does not reset if this occurs. After approximately 24 weeks of daily AR101 treatment at 300 mg in the Maintenance Period, Group 1 subjects will undergo a Post-Maintenance DBPCFC with a maximum dose of 2000 mg of peanut protein (4043 mg cumulative), according to the DPBCFC Schedule (Table 4). Subjects who do not tolerate \geq 300 mg peanut protein (443 mg cumulative) will be considered treatment failures and will be discontinued. Subjects who tolerate \geq 300 mg peanut protein (443 mg cumulative) will enter the EM and continue taking 300 mg/d of AR101 until the results of the alternate regimens explored in Group 2 subjects are known.

Table 4: DBPCFC Schedule (All Time Points)

DBPCFC Schedule (All Time Points)	
Challenge Dose, mg	Cumulative Dose, mg
3	3
10	13
30	43
100	143
300	443
600	1043
1000	2043
2000	4043

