7.4. CLASSIFICATION OF RESPONDER STATUS

7.4.1. Classification as a responder

To be a 600 mg responder at the EXIT DBPCFC, a subject must meet both of the following conditions:

- 1) Must have attained an MTD \geq 600 mg of peanut protein on Exit DBPCFC
- 2) Must not have experienced more than mild symptoms through 600 mg of peanut protein on Exit DBPCFC.

Classification as a 300 mg, a 2000 mg, and a 1000 mg responder are defined similarly.

A 600 mg responder is equivalent to tolerating \geq 1043 mg cumulative of peanut protein during their Exit DBPCFC. Likewise a 443 mg cumulative corresponds to a 300 mg responder, a 2043 mg cumulative dose corresponds to 1000 mg responder, and 4043 mg cumulative corresponds to a 2000 mg responder.

Responders at maintenance DBPCFC for Group 1 subjects are defined similarly.

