9.1.3. Maximum Severity of Symptoms at DBPCFC

Maximum severity of symptoms at the DBPCFC will be summarized at the 2000 mg, 1000 mg, and 600 mg levels. Symptom severity is determined according to the CoFAR scale at 5 levels: 1-Mild, 2-Moderate, 3-Severe, 4-Life Threatening, and 5-Fatal. Analysis is done on 4 levels: 0-None, 1-Mild, 2-Moderate, 3-Severe or higher (severe, life threatening, fatal). Subjects who experience no symptoms will be assigned a severity of 0-None. Symptom severity data is collected at each challenge dose of peanut protein during the DBPCFC (3 mg, 10 mg, 30 mg, 100 mg, 300 mg, 600 mg, 1000 mg, and 2000 mg). The maximum severity of symptoms observed in the DBPCFC at the specified dose (2000 mg, 1000 mg, or 600 mg) or lower will be used for each subject.

The number and percent of subjects will be presented by maximum severity for the specified challenge dose levels at the Exit DBPCFC for each group/cohort and at the maintenance DBPCFC for Group 1 for subjects who complete the maintenance DBPCFC.

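### The SAP's MTD rule for non-standard challenge doses ignores standard doses tolerated, so it scores too low when a higher standard dose was also tolerated and gives no value when no non-standard dose was tolerated

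*SAP*

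**What the plan says.** SAP Section 7.3 opens with a general definition: the MTD "is defined as the maximum single dose of peanut protein resulting in no more than mild symptoms and determined to have been tolerated". An exception follows. "If a subject is administered non-standard doses at a DBPCFC", the MTD becomes "the highest standard dose (whether administered or not) that is less than the highest tolerated non-standard dose".

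SAP Section 9.1.3 lists the challenge doses as "3 mg, 10 mg, 30 mg, 100 mg, 300 mg, 600 mg, 1000 mg, and 2000 mg", the same ladder as Protocol Section 3.1.4, Table 4. The next paragraph of SAP Section 7.3 leaves the 1 mg dose out of cumulative amounts, so that subjects who tolerate everything from 3 mg "or 1 mg to 300 mg have a cumulative MTD of 443 mg". The SAP does not define which doses are standard.

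Responder status depends on the MTD. SAP Section 7.4.1 begins "To be a 600 mg responder at the EXIT DBPCFC, a subject must meet both of the following conditions": an MTD of at least 600 mg, and nothing worse than mild symptoms through that dose. The 300, 1000 and 2000 mg levels are treated alike. The section also equates the 600 mg responder with tolerance of at least 1043 mg cumulative. Section 7.4.2 makes everyone else a non-responder at the level concerned.

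**The concern.** The exception is triggered by receipt of a non-standard dose, not by the non-standard dose being the highest one tolerated. Once triggered, it refers only to the highest tolerated non-standard dose. A subject who received an off-ladder dose and then went on to tolerate higher ladder doses is therefore scored from the off-ladder dose, and the later doses are lost. A subject whose only off-ladder dose was not tolerated has nothing to enter in the rule.

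The MTD feeds the 300, 600, 1000 and 2000 mg response rates and their exact intervals, the distribution of the highest tolerated dose (SAP Section 9.1.1) and the fold increase in MTD (Section 9.1.2). These are secondary efficacy outputs, and the cohorts are small enough for one subject to be visible in a rate.

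**Working it through.** **Inputs.** Ladder: 3, 10, 30, 100, 300, 600, 1000, 2000 mg (SAP Section 9.1.3; Protocol Table 4). Rule: SAP Section 7.3. Responder conditions: SAP Sections 7.4.1 and 7.4.2. Planned cohort sizes: Protocol Section 7.8.3.

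**The plan's own figures.** 3 + 10 + 30 + 100 + 300 = 443 mg. Adding 600, 1000 and 2000 in turn gives 1043, 2043 and 4043 mg. All agree with the SAP; with the 1 mg dose counted, the first sum would be 444 mg.

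**The rule as written.** If any non-standard dose was given, MTD = max{standard dose < highest tolerated non-standard dose}. The larger-of rule is MTD = max{highest tolerated standard dose, value from the written rule if it exists}. The sequences below are constructed examples; none comes from the documents.

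| Challenge (mg; all tolerated unless noted) | Highest tolerated non-standard dose | MTD as written | MTD, larger-of rule |
|---|---|---|---|
| 3, 10, 30, 100, 300, 450, 600, 1000 | 450 | 300 | 1000 |
| same, through 2000 | 450 | 300 | 2000 |
| 3, 10, 30, 200, 300, 600 | 200 | 100 | 600 |
| 3, 10, 30, 50, 100, 300 | 50 | 30 | 300 |
| 3, 10, 30, 100, 300, then 450 not tolerated | none | no value | 300 |
| 3, 10, 30, 100, 300, 700 (600 not given) | 700 | 600 | 600 |
| 3, 10, 30, 100, 300, 600, 1000, 1500 | 1500 | 1000 | 1000 |

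**Reading the table.**

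- Rows 1 to 4 show the error. In row 1 the subject tolerated 600 and 1000 mg but fails the MTD condition at both levels and is a non-responder at both.
- Row 1 also breaks the cumulative equivalence. Through the 600 mg step the subject tolerated 3 + 10 + 30 + 100 + 300 + 450 + 600 = 1493 mg, and the ladder doses alone sum to 1043 mg. Section 7.4.1 equates that with a 600 mg responder, yet the MTD of 300 mg denies it.
- Row 5 has no MTD, so Section 7.4.2 makes the subject a non-responder even at 300 mg, which was tolerated. The 0.3 mg convention in Section 9.1.2 is for subjects who tolerated no dose and does not fit.
- Rows 6 and 7 are the case in which the written rule works, and there the two rules agree.

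**Size per subject.** One false non-responder lowers a rate by 100/n points:

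- n = 50 (Cohort 2): 100/50 = 2.0
- n = 58 (175/3, one arm of Cohort 3): 100/58 = 1.7
- n = 120 (Cohort 1): 100/120 = 0.8

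With an assumed true count of 45/50 = 90% (exact 95% interval 78.2 to 96.7), one misclassified subject gives 44/50 = 88% (75.7 to 95.5) and two give 43/50 = 86% (73.3 to 94.2).

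**The case against.** The strongest reply is that the intent is clear. The general definition is the highest single dose tolerated, and the exception exists to bring an off-ladder maximum down to a ladder value; if the maximum is already on the ladder, nothing needs to be mapped. SAP Sections 3.2 and 9.1.1 describe the response endpoints as tolerating the stated dose, so a 600 mg non-responder who tolerated 600 mg would contradict them. Section 14 also plans independent confirmatory programming. This stands as evidence of what the authors meant, and a careful programmer may well apply it that way. It does not change what the sentence says, and two programmers working from the same sentence could differ or could both code it literally.

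It is also fair that the protocol prescribes one ladder for all time points, so non-standard doses may be rare, and that the error lowers response rates and so cannot flatter them. One qualification: the exception is worded for any challenge. If it were applied to the ARC003 Exit challenge, which is the baseline, a baseline MTD scored too low would make the change from baseline too large. The documents do not show how those baseline values were derived.

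A reader might go further and infer that the 1 mg paragraph contradicts the rule outright: 1 mg is off the ladder, no standard dose lies below it, and yet the SAP states that "1 mg to 300 mg have a cumulative MTD of 443 mg". The documents do not settle this. The paragraph is itself a specific provision for the 1 mg dose, it never calls that dose non-standard, and Section 9.1.2 refers for the challenge regimen to the ARC003 protocol, which is not among the documents. The contradiction exists only if 1 mg is labelled non-standard.

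**Conclusion.** As written, the exception gives a wrong MTD when a non-standard dose and a higher standard dose were both tolerated, and no MTD when no non-standard dose was tolerated. Both results conflict with the general definition in the same paragraph, and the first also conflicts with the cumulative equivalence in SAP Section 7.4.1. Neither conclusion depends on how the 1 mg dose is labelled.

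A reader might infer that every subject given a non-standard dose is badly misclassified. That does not follow: the rule is correct when the non-standard dose is the highest tolerated, which is probably the case its authors had in mind.

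The consequence is limited. The affected outputs are secondary and descriptive, SAP Section 6.4 plans no formal comparisons, and the primary endpoint, treatment-related adverse events, is untouched. The total effect cannot be computed because no frequency of non-standard doses is given. The 2-point shift per subject rests on the planned 50 of Cohort 2; the challenge summaries use completers aged 4 to 17 (SAP Section 9.1), and any smaller denominator makes the shift per subject larger. This is a small correction to a stated rule, worth making because it is nearly free.

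**What to change.** Replace the exception in SAP Section 7.3 with wording such as: if non-standard doses are given at a challenge, the MTD is the larger of (a) the highest standard dose given and tolerated and (b) the highest standard dose, given or not, below the highest tolerated non-standard dose, if there is one.

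Add a list of the standard doses and say whether 1 mg is among them.

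The cost is a sentence or two in the SAP and one line in the MTD derivation, ideally before database lock. No data collection changes, and subjects for whom the present rule already works keep their values.
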